Secondary: 
• To determine the volume of distribution (Vd) relative to the volume of infusion (Vi) for a convective infusion of autologous CSF into a deep brain nuclear region in humans• To determine the level of effectiveness or symptom response of infusion-enhanced, MRI-guided DBS.	
Methodology: Open-label, single-arm, quantitative study	
Number of subjects (planned): 4	
Diagnosis and main criteria for inclusion: Patients with Parkinson's disease and medically-refractory motor symptoms, who are already planned for MRI-guided DBS electrodes under general anesthesia.	
Investigational intervention: Unilateral infusion of 0.5 ml autologous CSF before DBS electrode insertion with MRI monitoring.	
Other study intervention(s): None	
Criteria for evaluation (i.e. endpoints):	
Efficacy: 
The primary efficacy assessment will be measured with the unmedicated UPDRS, motor subsection (part III) at 6 months in comparison to baseline. Additional efficacy endpoints will include standard, validated assessments of PD before and after DBS. Standard clinical measures of PD will be obtained as per usual clinical protocol at pretreatment baseline and 6 months postoperatively.
	
Safety: 
Safety will be assessed by incidence and severity of AEs, changes in physical examinations, neurological exams and the number of discontinuations due to AEs.
	
Distribution: 
Distribution will be assessed using MRI imaging to calculate the volume of distribution of autologous CSF into the basal ganglia in relation to the volume infused.
	

1. LIST OF ABBREVIATIONS	4
2. BACKGROUND AND RATIONALE	6
2.1. Study Synopsis	6
2.2. Disease Background.....	6
2.3. Case Study	7
2.4. Part 1 Preclinical Animal Studies	8
2.5. Part 2 Preclinical Animal Studies	11
3. STUDY OBJECTIVES.....	12
3.1. Primary Objectives.....	12
3.2. Secondary Objectives	12
4. SUBJECT ELIGIBILITY	13
4.1. Inclusion Criteria	13
4.2. Exclusion Criteria	13
5. TREATMENT PLAN.....	14
5.1. Study Overview.....	14
5.2. Treatment Assignment.....	14
5.3. DBS Surgery and Treatment Administration.....	14
5.4. Concomitant Medications/Treatments	17
5.5. Duration of Study Participation.....	18
5.6. Discontinuation/Withdrawal from Study.....	18
5.7. Subject Status Definitions	18
6. DEVICE INFORMATION	19
7. EVALUATION AND ASSESSMENTS.....	19
7.1. Schedule of Events	19
7.2. Study Assessments	20
7.3. Final Study Visit	22
7.4. Early Termination Visit	22
8. DATA ANALYSIS PLAN.....	22
8.1. Safety	22

1. LIST OF ABBREVIATIONS

Abbreviation or specialist term	Explanation
ACUC	Animal Care and Use Committee
AE	Adverse Event
BP	Blood Pressure
BUN	Blood Urea Nitrogen
CBC	Complete Blood Count
CED	Convection-Enhanced Delivery
CFR	Code Of Federal Regulations
CNS	Central Nervous System
CRF	Case Report Form
CSF	Cerebrospinal Fluid
CT	Computed Tomography
DBS	Deep Brain Stimulation
ECG	Electrocardiogram
FDA	Food And Drug Administration
GCP	Good Clinical Practices
GLP	Good Laboratory Practices
GPe	External Globus Pallidum
GPi	Internal Globus Pallidum
HCG	Beta-Human Chorionic Gonadotropin
HR	Heart Rate
h	Hour
I/E	Inclusion Exclusion Criteria
ICF	Informed Consent Form
ICH	International Conference On Harmonization
IRB	Institutional Review Board
IV	Intravenous
MRI	Magnetic Resonance Imaging
min	Minute
PD	Parkinson's Disease
PK	Pharmacokinetic
RR	Respiratory Rate
SAE	Serious Adverse Event
STN	Subthalamic Nucleus
UPDRS	Unified Parkinson's Disease Rating Scale
UVA	University of Virginia
Vd	Volume of distribution
Vi	Volume of infusion
WOCBP	Women of Childbearing Potential

2. BACKGROUND AND RATIONALE

2.1. Study Synopsis

This will be a small feasibility study investigating the safety and feasibility of infusion-enhanced, MRI-guided DBS electrode placement. We intend to enroll four (4) patients, with Parkinson's disease and medically-refractory motor symptoms, who are already planned for MRI-guided DBS electrodes under general anesthesia. Only a single side (nondominant) will be investigated with the research infusion when bilateral DBS electrodes are planned.

2.2. Disease Background

MRI-guided surgery was initially developed in the 1990s for a more precise brain biopsy.^{1,7} Recently, image-guided DBS has been proposed as an alternative to traditional electrophysiologically-guided DBS for medically-refractory Parkinson's disease.^{2,11,13-16,18} MRI-guided DBS can be performed under general anesthesia to avoid the discomfort of awake surgery and the need for prolonged unmedicated states. Clinical outcomes note improved off medication UPDRS motor scores by 60% and 49%, respectively which compares similarly to a recent meta-analysis of 34 studies estimating 52% in PD with STN DBS.⁹

True image-guided surgery adjusts to brain shifting during the procedure and the inherent registration errors that can be associated with image fusion techniques.^{4,8} Contemporary MRI continues to improve so that small stereotactic targets, that previously required intraoperative confirmation of their location with recordings or clinical testing, can now be directly visualized, however there is still room for improvement. McClelland et. al. analyzed electrodes placed using frame-based stereotaxy and microelectrode recording guidance, and found that 40 of 52 electrodes required re-positioning based on electrophysiologic localization.¹⁰ Unfortunately one can't determine whether this is from frame placement error, image fusion, MRI distortion, or stereotactic positioning error.

The assessment of DBS electrode placement relative to a selected target location in stereotactic space is relatively simple, requiring only postoperative imaging to compare with the preoperative plan. Real-time image-guided DBS placement has only recently been realized with compatible skull-mounted frames and high-field MRI. Radial vector error during DBS for PD has been measured at 1.2 ± 0.65 and 0.8 ± 0.4 mm.^{12,16} CT has also been used as a modality to guide asleep DBS surgeries although it is primarily used for image registration and confirmation of the placement as opposed to true image guided, localization during the procedure. Burchiel et al reported similar accuracies, but clinical outcomes are not yet available.²

Even with highly precise MRI-guided placement, the need for occasional electrode repositioning exists.¹⁶ This work was pursued on the assumption that improved resolution of these deep brain structures will aid stereotactic targeting, ultimately improving patient outcomes. We are interested to investigate if the combined use of intraoperative MRI-guided electrode placement, with improved target visualization from infusions, will improve patient outcomes as determined from UPDRS. The potential applicability of this technique to humans has many issues. First and foremost, the risk/benefit ratio must be favorable to ultimately consider infusion-enhanced, MRI-guided surgery as a valid surgical option. We perceive the addition of a small volume infusion (<0.5 ml) of autologous CSF to be associated with low morbidity. The increased risk of micro-catheter insertion should be similar or less than the current electrophysiological mapping process that requires multiple, sharp microelectrode penetrations. The safest infusate to test intuitively would be autologous CSF which is easily and safely obtained by lumbar puncture from patients who are already under general anesthesia.

Finally, the preclinical study described a proof-of-concept technique that mainly relies on the improved visualization of structures like the STN from T2 signal manipulation in the laboratory and clinic. Other structures like the internal segment of the globus pallidum or the ventral intermediate nucleus of the thalamus are better visualized with other MR sequences like inversion recovery or susceptibility-weighted images, respectively. In the future, we envision that infusion-enhanced MR imaging would be tailored to the desired brain target with target-specific sequences and infusates. For example, a choline-specific infusate could be designed to visualize the basal nucleus of Meynert if a neuroprotective or regenerative intervention were available for Alzheimer's disease. Imaging of all modalities will continue to improve with technology, but tailored intracerebral infusions may serve as an adjunct for improved visualization, not as a replacement for current imaging.

2.4. Part 1 Preclinical Animal Studies

2.4.1. Methods

Following UVA Institutional Animal Care and Use Committee approval (ACUC # 3843-08-10), Sus Scrofa Domestica (Yorkshire) female pigs weighing approximately 25 pounds were acquired and acclimated in the vivarium facility for 3 days. The CED swine experiments were performed with 3T MRI utilizing a standard human head coil.

Before surgery, the infusion apparatus was prepared. A PHD Ultra syringe pump (*Harvard Apparatus*, Holliston, MA, USA) was used with a 500 microliter, airtight, glass syringe. The syringe was connected to a series of four 60-inch extension sets (*Medex Micro Bore*, Product Code 536020, Smiths Medical, Dublin, OH, USA), each of which had 0.4 ml priming volume. The extension sets were then connected to an EViTAR microcatheter. (*NexGen Medical Systems, Inc.*, Reno, NV, USA). In experiments where normal saline was infused, the system was primed with normal saline via a 3-way valve at an extension set connection point. Care was taken to ensure there were no air bubbles. When CSF was infused, the priming was performed in the same manner after CSF had been obtained by lumbar puncture in the anesthetized animal.

On the day of surgery anesthesia was induced, and a T2 3T MRI was obtained in three orthogonal directions (*Siemens Trio* with Numaris 4 B17 software, TR 6000, TE 93, 2mm slice width, no gap, resolution 320x320). The mid-thalamic targets were identified on these pre-surgical MR images and then compared to a published swine stereotactic atlas.^{6,17} The coordinates for cannula placement were calculated and ranged in relation to the bregma: 0-3 mm anterior, 6-8 mm lateral, and 33-36 mm deep.

The animal was then positioned in a custom, MRI-compatible, stereotactic head frame such that the bregma and lambda points were aligned in the same plane. The scalp was then shaved and prepped with betadine, opened in linear fashion with a scalpel, and a small burr hole was created in the skull. After the dura was opened, the outer cannula of the infusion catheter, with a stylet, was then connected to the stereotactic manipulator and advanced to the target minus 1 cm in vector length (the infusion cannula is 1cm longer than the outer cannula). The outer cannula was then affixed to the skull. After removal of the stylet, the inner infusion microcatheter was then advanced through the outer cannula to the target. The PHD Ultra syringe pump was kept in the MRI control room and the tubing was passed through the wall. Sagittal, axial, and coronal T2 images were then obtained to verify the placement of the micro-catheter.

After MRI confirmation of the micro-catheter position, the infusion was instituted with rates between 1- 6 μ L/min so that convective distribution would be achieved. MRI monitoring was obtained at consistent 15 minute intervals for a total of 90-120 minutes depending on the rate of infusion. The volume of distribution (Vd) was obtained by using the average diameter of the infusion front as measured from T2 signal changes.

Following completion of micro-infusion experiments and MR imaging, the infusion catheter was removed and the scalp was sutured closed. Animals were recovered with direct observation for evidence of behavioral, neurologic, or gait dysfunction. Necropsy was performed at either early (48 hours), subacute (1 week), or late (1 month) time points. The brains were formalin fixed for sectioning, gross inspection, and histology with immunohistochemistry by a certified neuropathologist. A total of seven animals were infused: five with normal saline and two with CSF. The summary is shown below in Table 1.

Table 1: Summary of Swine CED Experiments

#	Infusate	Rate	Observation/ Histology (Days)
1	NS	1 μ l/min x 45min, then 3 μ l/min for 45 min, then 6 μ l/min for 30 min	2
2	NS	3 μ l/min x 90 min	28
3	NS	5 μ l/min x 90min	7
4	NS	5 μ l/min x 90min	28
5	NS	5 μ l/min x 90min	7
6	CSF	5 μ l/min x 90min	28
7	CSF	5 μ l/min x 90min	7

NS: Normal Saline, CSF: Cerebrospinal Fluid

2.4.2. Results

Volume of Distribution

The Vd/Vi, measured from T2 weighted MRI sequences varied from 2 to 4.5 regardless of the infusate. The rate for CED (as opposed to diffusion) is generally accepted as greater than 0.05 μ L per minute. These experiments infused between 1 to 6 μ L per minute without noticeable differences in the Vd/Vi. Total volume of infusion was bounded by either MRI time for low flow rates (limited to 90 minutes), or by observing no further increase in the volume of distribution when a pial boundary was encountered, and this ranged from 90 to 360 μ L.

MR Imaging

All MRI assessments were made from T2 weighted sequences. The CED infusions of normal saline or CSF became apparent with increased T2 hyperintensity after 30-45 μ L as infused. By 90 μ L, clear definition of nuclear structures began to develop. MRI changes in the infusion ceased when the infusion front reached the pial boundaries. CED infusions into the thalamus delineated the dorsomedial, ventral anterior, reticular, and centromedian nuclei – all of which were not apparent before the infusion (Figure 2). The enhanced appearance of the nuclear structures was consistent across animals with the ventral anterior and then the dorsomedial nucleus becoming the most apparent. Animal #7 had a post infusion scan performed 30 min after the completion of the infusion and the infusion effects persisted. Long term imaging was not performed.

[figure not shown]

Figure 2: (A) axial view of animal #1 after 360 μ L infusion of saline demonstrating the reticular nucleus is lateral to the VA nucleus, (B) axial view of animal #4 after 450 μ L of saline, (C) coronal view of animal #6 after 450 μ L CSF, and (D) axial time lapsed infusion of animal #3 at a rate 5 μ L / min. The white matter tract medial to the VA nucleus, lateral to DM, and anterior to CM is readily apparent after infusion.

Histology

Histology was examined at either early (within 2 days), subacute (7 days), or late (28 days) time points for evidence of acute or latent infusion toxicity. All specimens were analyzed with Hematoxylin and Eosin stains. Animals infused with normal saline demonstrated mild neuronal effects with pyknotic neurons and axonal retractions – possibly attributed to the tonicity of the infusate (Figure 3). **Those infused with autologous CSF had no evidence of neuronal change at either time point: 7 and 28 days.**

[figure not shown]

Figure 3: Hematoxylin and Eosin stains after convective infusion with normal saline identifying pyknotic neuron (dashed arrow) and axonal retraction figures (solid arrow) in a saline infused thalamus. These findings were not present when CSF infusion was performed.

2.5. Part 2 Preclinical Animal Studies

2.5.1. Purpose

Following the Part 1 preclinical animal studies, and FDA review, further infusions were performed to validate that there was no toxicity related to the infusion of CSF. A control site was included for comparison. The infusion catheter planned for the human trials was used in the Part 2 preclinical animal studies (SmartFlow™ K123605).

2.5.2. Methods

Following UVA Institutional Animal Care and Use Committee approval (ACUC # 3843-08-16), Sus Scrofa Domestica (Yorkshire) female pigs weighing approximately 25 pounds were acquired and acclimated in the vivarium facility for 3 days.

On the day of surgery anesthesia was induced and a spinal tap was performed under fluoroscopic guidance. Five milliliters of CSF were removed and saved for later to be infused. The animal was then positioned in a custom stereotactic head frame such that the bregma and lambda points were aligned in the same plane. The scalp was then shaved and prepped with betadine, opened in linear fashion with a scalpel, and a small burr hole was created in the skull bilaterally 6mm lateral to the bregma. After the dura was opened, the infusion catheter (SmartFlow™ K123605) was advanced into the brain 30mm in the right thalamus then retracted (control site). It was then advanced 30mm in the left thalamus for the CSF infusion.

The previously acquired CSF was used to prime the infusion system. A Harvard Apparatus PHD Ultra infusion pump was used with a piece of extension tubing (*Medex Micro Bore*, Product Code 536020, Smiths Medical, Dublin, OH, USA) and a 500 microliter airtight gas syringe. The CSF was filtered with a 0.1 micron in-line filter while priming the system. CSF was then infused in the left thalamus at a rate of 5 microliters / min for a total volume of 450 microliters. The infusion catheter was then withdrawn, the wound was closed, and the animal was taken to recovery.

Nine animals in total were infused with autologous CSF. Five animals underwent necropsy at 24 hours and 4 animals underwent necropsy at 28 days. Necropsy was performed by removing the brain immediately following euthanasia via a craniectomy and placing the whole brain in 10% buffered formaldehyde.

After a minimum of 2 weeks the formalin fixed brains were cut, H&E stained, and analyzed by an independent neuropathologist.

2.5.3. Results

Histology results are summarized below. None of the CSF infusion sites had evidence of toxicity. Distinct tracts were identified in eight of the nine brains. In the brain where a tract was not identified, the thalamus was sectioned forty times in 5-micron thicknesses. After sectioning, slides were H&E stained then reviewed. All tracts showed typical findings of catheter insertion into brain (microhemorrhage at 24 hours; gliosis and hemosiderin deposition at 1 month). There was evidence of axonal injury in one acute animal control tract, consistent with severing of axons from the insertion of the CED catheter. The neuropathology report is attached as attachment 2.0.

	Animal #	CSF Infusion	Control
Acute (24 hours)	1	No neuronal injury, distinct track identified	Axonal swelling, distinct track identified
	4	No neuronal injury, distinct track identified	No neuronal injury, distinct track identified
	5	No neuronal injury, distinct track identified	No neuronal injury, distinct track identified
	8	No neuronal injury, distinct track identified	No neuronal injury, distinct track identified
	9	No neuronal injury, distinct track identified	No neuronal injury, distinct track identified
Chronic (1 month)	2	No neuronal injury, distinct track identified	No neuronal injury, distinct track identified
	3	No neuronal injury, no distinct track identified	No neuronal injury, no distinct track identified
	6	No neuronal injury, distinct track identified	No neuronal injury, distinct track identified
	7	No neuronal injury, distinct track identified	No neuronal injury, distinct track identified

3. STUDY OBJECTIVES

The proposed study will evaluate safety foremost but also the distribution and initial effectiveness of infusion-enhanced, MRI-guided DBS for patients with medication-refractory, Parkinson's disease.

3.1. Primary Objectives

Safety:

Safety of the CSF infusion will be evaluated using a common description of clinical complications for patients treated in this study. Safety will be determined by an evaluation of the incidence and severity of infusion-related side effects and complications from the first treatment day visit through the 6-month post-treatment time point. All AEs will be reported and categorized by investigators as definitely, probably, possibly, unlikely, or unrelated to the CSF infusion, and/or Parkinson's disease progression. Safety will be assessed by incidence and severity of AEs, changes in physical examinations, neurological exams, and the number of discontinuations due to AEs

3.2. Secondary Objectives

Distribution:

The volume of distribution (Vd) will be determined immediately following the infusion (Vi) with intraoperative 1.5T MRI, T2-weighted sequences. The distribution of the infusion by convective properties in a deep brain human nucleus (GPi or STN) will be determined by calculating the Vd/Vi ratio.

Efficacy:

The primary efficacy assessment will be measured with the unmedicated UPDRS, motor subsection (part III) at 6 months in comparison to baseline. Additional efficacy endpoints will include standard, validated assessments of PD before and after DBS. Standard clinical measures of PD will be obtained as per usual clinical protocol at pretreatment baseline and 6 months postoperatively. These DBS-related assessments include:

- UPDRS in the off and on medication state
- Levodopa medication equivalents (milligrams)
- Neuropsychological assessment
- PDQ-39

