5.3.3. Infusion Procedure

Once the patient is positioned within the MRI, the dura is sharply punctured with a sharp, ceramic stylet, and the MR-compatible infusion catheter is inserted. A second MRI is obtained to confirm the catheter position.

The research infusion of autologous CSF is initiated at 5 microliters/minute. Serial MRI monitoring of the infusion is obtained with T2 weighted images at approximately 15 minute intervals until the target nucleus can be visualized or until a total of 500 microliters is administered. The research infusion could add up to an additional 100 minutes to the patient's DBS surgery. MR imaging of the research infusion and then clinical assessment of the DBS electrode placement will be conducted on a 1.5T Siemens Espre system with continuous monitoring of both SAR and B1+rms values.

A Medfusion 3500 syringe infusion pump with a 1.0 milliliter BD glass syringe will be used with extension tubing (*Medex Micro Bore*, Product Code 536020, Smiths Medical, Dublin, OH, USA). The infusion catheter will be the SmartFlow™ K123605 (*MRI Interventions*).

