6. DEVICE INFORMATION

Description

The agent under investigation is an intracerebral infusion of autologous CSF. The autologous CSF will be obtained via lumbar puncture and administered during the same procedure, so there is no need for storage of the CSF.

Agent Preparation and Administration

A lumbar puncture will be performed to obtain 10 ml of autologous CSF. This will be passed through a sterile 0.1 micron filter and maintained sterile. A disposable, MRI-compatible frameless stereotactic system that is employed for MRI-guided DBS surgery under general anesthesia will be secured to the patient's skull. Once the patient is positioned within the MRI, the dura is sharply punctured with a sharp, ceramic stylet, and the MR-compatible infusion catheter is inserted.

The research infusion of autologous CSF is initiated at 5 microliters/minute. Serial MRI monitoring of the infusion is obtained with T2 weighted images at 15 minute intervals until the target nucleus can be visualized or until a total of 500 microliters is administered. Any remaining CSF will be disposed of at the end of the procedure.

A Medfusion 3500 syringe infusion pump with a 1.0 milliliter BD glass syringe will be used with extension tubing (*Medex Micro Bore*, Product Code 536020, Smiths Medical, Dublin, OH, USA). The infusion catheter will be the SmartFlow™ K123605 (MRI Interventions).

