8. DATA ANALYSIS PLAN

For this study, the Safety and Effectiveness assessment will be descriptive with no statistical endpoints. The results will be examined and analyzed and used as a basis for determining the nature of future studies. Formal hypothesis testing for efficacy is not proposed for this initial safety and preliminary efficacy trial.

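### Vd is read once, at a stopping volume that differs by subject; reading it on the T2 scans already planned would show whether it was still growing

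*Combined protocol and SAP*

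**What the plan says.** Section 3.2 defines the distribution measure: "The volume of distribution (Vd) will be determined immediately following the infusion (Vi) with intraoperative 1.5T MRI, T2-weighted sequences". The result is expressed as Vd/Vi. That is one reading per subject, at the end of the infusion.

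Section 5.3.3 sets the rate at 5 microliters/min, with T2 scans roughly every 15 minutes "until the target nucleus can be visualized or until a total of 500 microliters is administered". Section 6 repeats the rule: "Serial MRI monitoring of the infusion is obtained with T2 weighted images at 15 minute intervals until the target nucleus can be visualized", with the same cap. The synopsis gives 0.5 ml as if it were fixed, and Table 2 in Section 5.3.1 gives less than 0.5 ml. The procedure text is the operative one, and it lets Vi vary. Nothing in the protocol says that the serial images will be used to measure Vd.

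The swine results in Section 2.4.2 bear on this. On imaging: "MRI changes in the infusion ceased when the infusion front reached the pial boundaries". On volume: "Total volume of infusion was bounded by either MRI time for low flow rates (limited to 90 minutes), or by observing no further increase" in Vd at a pial boundary. The ratio, "measured from T2 weighted MRI sequences varied from 2 to 4.5 regardless of the infusate". Serial imaging was also done in those animals (Section 2.4.1): "MRI monitoring was obtained at consistent 15 minute intervals for a total of 90-120 minutes depending on the rate of infusion".

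Section 8 says that "the Safety and Effectiveness assessment will be descriptive with no statistical endpoints" and does not mention Vd/Vi.

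**The concern.** A ratio to each subject's own Vi adjusts for delivered volume only while Vd keeps rising in proportion to Vi. Once Vd stalls, Vi goes on rising and the ratio falls, although convection up to that point was no worse. The human procedure ends on visualization or at the cap; it has no stop for a stalled Vd.

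With four subjects, four end ratios would be the whole stated result for this objective. If a subject who ran to 500 microliters shows a lower ratio than one who stopped early, the end reading alone leaves two explanations open: poorer convection, or a front that had stopped advancing. They point to different choices of infusion volume in a later study, and informing later studies is what Section 8 says the results are for.

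**Working it through.** **Inputs.** Rate 5 microliters/min, scan interval about 15 min, cap 500 microliters (Sections 5.3.3 and 6). Swine Vd/Vi 2 to 4.5 (Section 2.4.2). Four subjects (Section 8.4).

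**The plan's own figure.** Section 5.3.3 says the infusion may add up to 100 minutes. Cap / rate = 500 / 5 = 100 min, which agrees.

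**Possible stopping volumes.** Vi = 5 x scan time. Scans at 15, 30, 45, 60, 75 and 90 min give 75, 150, 225, 300, 375 and 450 microliters; the cap of 500 comes at 100 min. The permitted range is 500 / 75 = 6.7-fold. A full infusion offers six serial scans plus the end reading, 7 in all. A stop at 150 offers two readings, and a stop at 75 only one.

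**Effect of a plateau (assumption).** Let Vd grow at ratio r and stop growing at infused volume P. Then end ratio = r x min(Vi, P) / Vi. The documents give no P for humans. The values 450 and 360 are swine total infused volumes, used only for illustration. At Vi = 500:

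| P | End ratio | r = 2 | r = 3 | r = 4.5 |
|---|---|---|---|---|
| none by 500 | r | 2.00 | 3.00 | 4.50 |
| 450 | 0.90r | 1.80 | 2.70 | 4.05 |
| 360 | 0.72r | 1.44 | 2.16 | 3.24 |

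The size depends on the assumption. If instead Vd is capped at an assumed 1000 microliters with r = 3, the ratio at 500 is 1000 / 500 = 2.0. With a cap of 1500 it is 1500 / 500 = 3.0, no effect.

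**What one reading cannot separate and a series can.** Take subject A with r = 2.16 and no plateau, and subject B with r = 3 and P = 360. Vd in microliters:

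| Vi | A: 2.16 x Vi | B: 3 x min(Vi, 360) |
|---|---|---|
| 75 | 162 | 225 |
| 150 | 324 | 450 |
| 225 | 486 | 675 |
| 300 | 648 | 900 |
| 375 | 810 | 1080 |
| 450 | 972 | 1080 |
| 500 | 1080 | 1080 |

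Both end at 1080 / 500 = 2.16. The gain in Vd per microliter infused stays at 2.16 in A. In B it is 3.0 up to 300, then (1080 - 900) / 75 = 2.4, then 0.

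**Can the swine range settle it?** Table 1 totals are 45 + 135 + 180 = 360 microliters (animal 1), 3 x 90 = 270 (animal 2) and 5 x 90 = 450 (animals 3 to 7). Section 2.4.2 gives 90 to 360. Neither says at what Vi each ratio was read. At 450 with P = 360 the model gives 0.8r, so r from 2 / 0.8 = 2.5 to 4.5 / 0.8 = 5.6 would produce the reported 2 to 4.5. The swine range neither shows nor excludes such a plateau.

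**The case against.** The strongest reply is that the harm is hypothetical. The boundary effect was seen in the thalamus of pigs of about 25 pounds, and nothing in the protocol places such a boundary within reach of an infusion into human GPi or STN. Without one, the effect is zero. This stands, and it limits the point to a precaution.

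The 6.7-fold range is also what the rule permits, not what should be expected. In swine, nuclei began to be clearly defined by 90 microliters, so stops may cluster early, below any plateau assumed here. That is fair, although inclusion criterion 4 already requires a visible target and the protocol sets no threshold for the visualization stop, so the spread cannot be predicted.

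It can also be said that the images will exist anyway and could be measured later. True: Section 3.2 does not forbid it. But nothing commits the team to it, and reading back only when a ratio looks odd is weaker than reading every subject the same way.

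The series has limits too. It shows growth only with two or more measurable scans. Swine signal appeared only after 30 to 45 microliters, so early human scans may be unreadable. A plateau at 450 would show only between the last two readings. The human method of measuring Vd is not stated beyond the sequence, but that applies equally to the single reading.

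A reader might infer from Section 8's silence that distribution has no analysis at all. The documents do not support that: Section 3.2 gives the quantity, timing, sequence and ratio, and for a descriptive study of four the absent paragraph is only missing detail. Nor is a varying Vi a defect in itself.

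**Conclusion.** The point holds as a cheap improvement. The end-of-infusion ratio is a legitimate endpoint. It is open to two readings only if Vd stops growing before the infusion ends, and the scans that could show this are already planned.

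The size is conditional: nothing if no plateau is reached; 10% lower at 500 microliters if growth stops at 450; 28% lower if it stops at 360. A reader might take these as estimates of bias in this trial. They are not: both values of P are assumed, and the documents give no human plateau volume. The effect is on interpretation of a secondary, descriptive endpoint. No error rate, sample size or decision rule is involved.

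**What to change.** In Section 3.2, add wording such as:

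> Vd will be measured by the same method on each serial T2-weighted scan and immediately after the infusion. The end-of-infusion Vd/Vi ratio is the distribution endpoint. For each subject we will report Vd against Vi at every measurable scan, the delivered volume, the reason for stopping (target visualized or 500 microliters reached) and the target (GPi or STN). Scans on which the infusion cannot be delineated will be listed as not measurable. A subject who stops at the first scan contributes no information on growth.

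I would not add a ratio at a volume common to all subjects. That volume could be as low as 75 microliters, below the 90 at which swine nuclei began to be clearly defined, so it would add little.

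The cost is at most 7 readings per subject instead of 1, or 7 x 4 = 28 in all instead of 4, some of which may prove unreadable. It needs no extra scan, procedure, visit or subject.
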